### Data Collection:

Data collection will involve objective measures and participant-reported outcomes. The assessment will include wound healing progress, scar appearance, pain levels, and patient satisfaction. These parameters will be assessed at predetermined intervals using standardized assessment tools and scoring systems.

### Sample Size Calculation:

A sample size calculation has been performed to determine the required number of participants in each age and BMI stratum based on the expected effect size and statistical power.

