### 6. Study Methodology

The proposed study is a prospective, randomized controlled trial (RCT) that aims to compare the effectiveness of two topical treatments, HM Gel (Hydrophilic Methacrylate Gel) and BS Ointment (Beta Sitosterol Ointment), in promoting the healing process of episiotomy and cesarean section scars. The study will include two groups: an experimental group receiving HM Gel and a control group receiving BS Ointment.

**Sample size calculation or justification of numbers:** A priori sample size calculation will be conducted to determine the required number of participants for adequate statistical power. This calculation will consider factors such as the expected effect size, desired level of significance, power of the study, and anticipated dropout rate. We aim to recruit enough participants to ensure the statistical validity and generalizability of the study results.

The sample size for this study was determined based on the desired level of statistical power (80%) and the significance level (0.05). Since no prior estimates of effect size were available, a moderate effect size was assumed. Using a two-sample t-test, the sample size per group was calculated to be 53 participants in patients with cesarean section. Considering rounding up to the nearest whole number, a total sample size of

106 participants was determined for the 2 groups of cesarean section, and the same number for patients (53) with episiotomy, a total of 106 participants was determined for the 2 groups of vaginal delivery with episiotomy. This sample size calculation ensures that the study will have sufficient power to detect meaningful differences in pain levels and wound healing outcomes.

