## HMC RESEARCH PROTOCOL

address this concern and to ensure the robustness of our findings, we have factored in an anticipated dropout rate of 10% in our sample size calculation. While this rate is conservative and aligned with similar clinical trials, we understand the importance of minimizing the impact of dropout on our study's outcomes.

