### 10. Statistical Consideration and Data Analysis :

#### Randomization and Allocation Concealment:

We will be blinding the tube ointments to ensure impartiality in the assessment of efficacy between the two treatments. This adjustment will enable us to minimize potential biases and ensure the integrity of our results.

The ointment tubes will be packaged in identical outer packaging, such as opaque boxes, to conceal any distinguishing features.

This approach will ensure that the participants nor the assessors of wound know which ointment is being used. Blinding of data analysts will help ensure impartiality during the analysis process.

Randomization: We will indeed use computer-generated random numbers or randomization software to ensure unbiased and unpredictable allocation. Instead of stratifying during randomization, we will collect comprehensive data on age group, BMI, and type of surgery. Subgroup analyses will be conducted during data analysis, allowing for a thorough examination of treatment effects within specific subgroups.

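### The protocol says a sample size was calculated for each age and BMI stratum, but the only calculation shown is per surgery type, and the planned numbers would not power crossed age-by-BMI strata

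*Combined protocol and SAP*

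**What the plan says.** Section 7, under Sample Size Calculation, reports as completed work: "A sample size calculation has been performed to determine the required number of participants in each age and BMI stratum". It adds that this rests on the expected effect size and power, but it gives no stratum, no cut-point and no number.

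The only calculation with figures is in section 6: "Using a two-sample t-test, the sample size per group was calculated to be 53 participants in patients with cesarean section". The same number is then used for episiotomy, where "a total of 106 participants was determined for the 2 groups of vaginal delivery with episiotomy". The stated power is 80% and the significance level 0.05. On the effect size the protocol says: "Since no prior estimates of effect size were available, a moderate effect size was assumed". The Dropout Rate paragraph states that "we have factored in an anticipated dropout rate of 10% in our sample size calculation", and the Sample Size Adjustment paragraph raises recruitment to about 60 per group. None of this text mentions age or BMI.

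The statements on stratification differ. The opening of section 7 stratifies randomization by age and BMI. The Stratification paragraph of the same section names surgery type as a stratification factor. Section 10, under Randomization and Allocation Concealment, says: "Instead of stratifying during randomization, we will collect comprehensive data on age group, BMI, and type of surgery", with subgroup analyses to follow. The Subgroup Analyses paragraph of section 10 names age, BMI and parity as possible effect modifiers and allows either interaction tests or stratified analyses.

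**The concern.** The protocol claims a design property, adequate numbers in every age and BMI stratum, that nothing else in it supports. The sentence fits the age-and-BMI stratified randomization at the start of section 7, which section 10 then withdraws.

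What is at stake is how the subgroup results are read. Section 10 plans age and BMI analyses on primary and secondary outcomes, with one significance threshold of 0.05 and no statement on multiplicity. A reader or ethics committee that takes the section 7 sentence at face value could treat a null result in a stratum as evidence of no effect, although that stratum may have had little chance of showing one. The main comparison within each surgery type is not affected.

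**Working it through.** **1. Inputs from the protocol.** Two-sample t-test, 80% power, significance level 0.05, 53 per arm in each surgery type (section 6); 10% dropout; about 60 per group after adjustment.

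**2. Assumptions, because the protocol is silent.**
- The test is two-sided.
- 'Moderate' means a standardised difference d of 0.5. I also use the value of d that reproduces 53.
- 'Group' means each of the four surgery-by-treatment groups, so the total is 4 × 60 = 240. The protocol states no total after the adjustment; before it, 4 × 53 = 212.
- Strata are crossed (age by BMI), equal in size and allocated 1:1. Their number k is not given, so I use 4 (2 × 2), 6 (2 × 3) and 9 (3 × 3).

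**3. The protocol's own figure.** The normal approximation is n per arm = 2(z₀.₉₇₅ + z₀.₈₀)² / d².
- At d = 0.5: 2 × (1.960 + 0.842)² / 0.25 = 62.8, so 63; the exact t calculation gives 63.8, so 64. Neither is 53.
- Solving the two-sided t calculation for n = 53 gives d = 0.549, or about 0.55.
- A one-sided test at d = 0.5 gives 50 (normal) or 51 (t), also not 53.
- Dropout: 53 / 0.90 = 58.9, so 59, which agrees with about 60.

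I therefore report results at both d = 0.5 and d = 0.55.

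**4. Power per crossed stratum.** The number per arm is N / (2k). Power comes from the noncentral t distribution with 2n − 2 degrees of freedom and noncentrality d√(n/2).

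| Basis | Strata | Per arm | Power, d = 0.5 | Power, d = 0.55 |
|---|---|---|---|---|
| Pooled over surgery types, N = 240 | 4 | 30 | 48% | 55% |
| | 6 | 20 | 34% | 40% |
| | 9 | 13.3 | 24% | 28% |
| One surgery type, N = 120 | 4 | 15 | 26% | 31% |
| | 6 | 10 | 19% | 21% |
| | 9 | 6.7 | 13% | 15% |

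With 10% dropout, four pooled strata have 27 per arm, and power is 44% (d = 0.5) or 51% (d = 0.55).

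**5. Total needed for 80% power in every stratum, before dropout, pooled over surgery types.**
- At the protocol's own 53 per arm: 106 × 4 = 424 women for four strata.
- At 64 per arm (d = 0.5): 128 × 4 = 512.
- The plan has 212 to about 240. The 424 figure does not depend on my choice of effect size or sidedness, because it uses the protocol's own 53.

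**6. The less demanding reading: age levels and BMI levels taken separately.** One factor with two equal levels, pooled over surgery types, leaves 240 / 4 = 60 per arm in each level. Power is then 78% at d = 0.5 and 85% at d = 0.55; with 10% dropout (54 per arm), 73% and 81%. One factor with three equal levels leaves 240 / 6 = 40 per arm, with power of 60% and 68%.

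**The case against.** A reader might infer that power is low in any age or BMI stratum, and that 212 to 240 women could not support the claim however it is read. The documents do not go that far. The protocol defines no strata, so its sentence can also mean age levels and BMI levels taken one at a time; step 6 shows that a single two-level factor pooled over surgery types comes near or above 80%. A very uneven split could also leave one large stratum with enough women: about 128 of 240 at d = 0.5, or 106 at d = 0.55. What does not survive is the claim for each crossed stratum, since even four cells at 53 per arm need 424.

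A reader might also infer that no stratum calculation was ever done. The documents show only that none is reported.

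Three further points stand:
- The t-test figures do not describe the chi-square or Fisher test planned for wound healing, for which no healing rates are given. Nor do they describe an interaction test.
- At d = 0.5 the section 6 figure of 53 is not reproduced, and the totals required are about a fifth higher than at 53 per arm (512 against 424).
- Section 10 already says that the subgroup analyses are there to explore effect modifiers, and no confirmatory claim in an age or BMI stratum is planned. This lessens the risk of over-interpretation. It does not remove the unsupported sentence in section 7, which points the other way.

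**Conclusion.** The point holds as an internal inconsistency. A stratum-level sample size is asserted and none is shown; the one calculation shown is per surgery type; no strata are defined; and section 10 withdraws the stratification on which the sentence seems to rest. That much needs no assumption.

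The size of the shortfall is conditional on the assumptions in step 2. For equal crossed strata, power runs from 24% to 55% pooled over surgery types and from 13% to 31% within one surgery type, across 4 to 9 strata and both values of d. If about 60 per group meant only two groups overall, the numbers would be lower still. The power shortfall should not be stated for every possible definition of a stratum.

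This should be corrected, but it does not threaten the main comparison.

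**What to change.** Replace the Sample Size Calculation sentence in section 7 with:

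> The sample size was calculated per surgery type only (section 6). Age and BMI subgroup analyses are exploratory and are not powered.

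Carry the same label into the Subgroup Analyses paragraph of section 10. Reconcile the opening of section 7, its Stratification paragraph and the randomization text in section 10, so that the protocol says once whether randomization is stratified and by what.

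If the sponsor does hold a stratum-level calculation, showing it with defined age and BMI categories would also resolve the point.

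The cost is protocol wording and a less favourable statement about subgroup power. No extra enrolment is proposed.

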### Study Location:

This study will take place at Al-Wakra hospital.

## 8. Study procedures

We plan to start the study as soon as MRC approval is obtained, and MRC approval letter is issued. The expected length of the study is one year.

Following MRC approval, we will start to stratify and recruit the patients based on inclusion

## HMC RESEARCH PROTOCOL

and exclusion criterias . A research code (e.g. YK001) will be assign topatient to ensure privacy. A separate sheet will be kept with the PI including identifier date for each code). One of the investigators will then record the patients for inclusion. They will then be assigned the subject number code and the study variables will be recorded in a separate excel file under the patient's subject code.

- Study is expected to last 12 months (01/11/2023 -01/11/2024).

### **Timeline:**

- Submission and approval of study (2 months)
- Data collection, cleaning, and analysis (5 months)
- result collation, interpretation, writing of manuscripts and dissemination (5 months).

### **Informed Consent**

Yes (attached)

### **9. Risk**

All collected data will be coded so as to avoid any risk of confidentiality breach.

**Here are some potential anticipated risks to consider:**

- Allergic reactions: Some participants may experience allergic reactions to the topical treatments, HM Gel, or BS Ointment. Allergic reactions can range from mild skin irritation to more severe symptoms, such as rash, itching, or swelling.
- Skin irritation: As with any topical treatment, there is a possibility of skin irritation at the application site. Participants may experience redness, itching, or discomfort around the wound area.
- Delayed wound healing: There is a small possibility that the application of the treatments may interfere with the natural wound healing process, leading to delayed wound closure or complications in some participants.
- Unsatisfactory scar appearance: Despite the use of the treatments, some participants may not achieve the desired cosmetic outcomes in scar appearance. This could potentially impact patient satisfaction with the treatment.
- No treatment effect: It's possible that neither treatment (HM Gel or BS Ointment) may demonstrate a significant effect on wound healing or scar management, leading to no substantial improvement in the participants' conditions.

## HMC RESEARCH PROTOCOL

- Infection: Although both treatments are topical and not invasive, there is still a small risk of infection at the wound site due to various factors, such as inadequate wound care or microbial contamination.

Participants will be informed of these potential risks during the informed consent process, allowing them to make an informed decision about their participation in the research.

### Bio-Specimens & Sample Collection

Not applicable

### Outcomes

- 1- The primary outcome of this trial is to assess the effectiveness of Hydrophilic Methacrylate Gel (Hemagel) in promoting wound healing and reducing complications in patients undergoing episiotomy or cesarean section procedures. Specifically, we aim to compare the rate and quality of wound healing between the group receiving Hemagel Ointment and the control group.
- 2- The secondary outcome includes evaluating the impact of Hydrophilic Methacrylate Gel on pain management, scar appearance, and patient satisfaction. We will assess pain levels using standardized pain scales and compare the effectiveness of Hemagel Ointment in alleviating pain compared to the control group. Additionally, scar appearance will be evaluated using validated assessment tools to determine if Hemagel Ointment leads to improved cosmetic outcomes. Patient satisfaction will be assessed through questionnaires to gauge the subjective experience and level of satisfaction with the treatment.

By achieving these objectives, this trial aims to provide evidence regarding the effectiveness of Hydrophilic Methacrylate Gel in promoting wound healing, managing pain, improving scar appearance, and enhancing patient satisfaction in the context of post-episiotomy and cesarean section scar.

### Data Collection & Confidentiality

The patients name, medical record number and subject number will be recorded in a separate file. This file will be kept on a password locked computer at PIs office at pharmacy department of Al Wakra hospital.

The assigned subject number will be used to record all the study variables. No physical copies will be used and data will not be shared outside HMC.

## HMC RESEARCH PROTOCOL

The principal investigator will control access to this study's data.

Once patients are chosen, Cerner database will be reviewed for details pertinent to the study.

The data will be collected as per the data collection sheet, which is attached for review. The PI is the one to collect the data in excel sheet and stored in a soft copy.

Access for data collected will be under control of the principal investigator.

Data will be collected de-identified, codes will be used to cover patient identifiers such as Name, HC no., DOB. Any link between code and identifier will be deleted at the end

## HMC RESEARCH PROTOCOL

of the data collection and anonymized data will be kept for at least 5 years after study completion. Following MRC approval, a research code (e.g. YK001) will be assign to patient to ensure privacy. A separate sheet will be kept with the PI including identifier date for each code). One of the investigators will then record the names and medical record numbers of the patients for inclusion. They will then be assigned the subject number code and the study variables will be recorded in a separate excel file under the patient's subject code.

The linking sheet to the subject's identifier will be kept in a secure locked place in the PI office and will be destroyed after data collection and will not be shared outsideHMC. Data have to be stored for 5 years post study completion.

### Subject Withdrawal/ Withdrawal of Consent

In this study, participants have the right to withdraw from the trial at any time without providing a reason. Withdrawal of consent will not affect their current or future medical care. Participants who decide to withdraw from the study will be informed that they are free to do so without any negative consequences. Their decision to withdraw will be respected, and their data collected up to the point of withdrawal will be retained and included in the analysis, unless they specifically request their data to be removed.

To ensure proper handling of participant withdrawal, the study team will clearly communicate the withdrawal process during the informed consent process. Participants will be provided with contact information for the study coordinator or principal investigator, who will be available to answer any questions or concerns related to the study or the withdrawal process.

If a participant decides to withdraw their consent, their study participation will be terminated immediately. Any unused investigational product (HM Gel or BS Ointment)will be collected, and no further assessments or interventions will be performed on the participant.

The reasons for withdrawal, if provided voluntarily by the participant, will be recordedto inform the study team of potential issues and ensure continuous improvement of the research process.

Participant confidentiality will be strictly maintained throughout the study and beyond. All data obtained from participants who withdraw their consent will be handled withthe utmost confidentiality and will not be disclosed in any study-related publications or presentations.

It is important to emphasize that participant withdrawal is entirely voluntary, and participants will be assured that their decision will not impact their relationship with the

## HMC RESEARCH PROTOCOL

healthcare providers or Al-Wakra hospital in any way. Their safety and well-being will remain a top priority throughout the study, regardless of their decision to continue or withdraw from the trial.

### 10. Statistical Consideration and Data Analysis :

#### Randomization and Allocation Concealment:

We will be blinding the tube ointments to ensure impartiality in the assessment of efficacy between the two treatments. This adjustment will enable us to minimize potential biases and ensure the integrity of our results.

The ointment tubes will be packaged in identical outer packaging, such as opaque boxes, to conceal any distinguishing features.

This approach will ensure that the participants nor the assessors of wound know which ointment is being used. Blinding of data analysts will help ensure impartiality during the analysis process.

Randomization: We will indeed use computer-generated random numbers or randomization software to ensure unbiased and unpredictable allocation. Instead of stratifying during randomization, we will collect comprehensive data on age group, BMI, and type of surgery. Subgroup analyses will be conducted during data analysis, allowing for a thorough examination of treatment effects within specific subgroups.

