## 3. Introduction / Background

Episiotomy and cesarean section (CS) are common surgical procedures in obstetrics and gynecology, often performed to safeguard the well-being of both mothers and newborns (1). Adequate wound healing and effective scar management are vital components of postoperative care, profoundly influencing patient recovery, comfort, and long-term quality of life (2). However, despite the significance of these aspects, the current body of literature presents a noticeable gap in real-world evidence regarding the effectiveness of topical treatments specifically tailored for post-episiotomy and CS scars.

The absence of well-established treatment protocols, coupled with the limited research in this area, presents significant challenges for healthcare professionals tasked with selecting the most suitable interventions for scar management. Current standard practices typically involve the use of emollients, moisturizers, and silicone-based products (3). However, the empirical evidence supporting their efficacy in promoting wound healing and enhancing patient satisfaction remains inconclusive (4, 5).

In the specific context of Al-Wakra Hospital, we conduct an average of approximately 350 deliveries each month, which includes both cesarean sections and normal deliveries with episiotomy procedures. This significant volume of procedures highlights the relevance and importance of investigating the most effective scar management interventions.

In our standard clinical practice at Al-Wakra Hospital, emollient, moisturizer such as betasitosterol is commonly used for scar management.

The local healthcare system in Qatar and Al-Wakra Hospital is committed to providing the highest standard of care to its diverse patient population. Given the substantial number of patients undergoing episiotomy and cesarean section procedures, optimizing scar management is imperative to improve patient outcomes and enhance overall healthcare quality.

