### **Details of the interventions (not procedures) involved in the research:**

The study involves the application of two topical treatments, HM Gel and BS Ointment, to the respective treatment groups. The application of these treatments will follow established protocols. The study does not involve any invasive procedures.

The administration of the assigned treatments will be administered in routine clinical practice following the surgical procedure, either episiotomy or cesarean section, and continue for a period of two weeks. During this period, the participants will be instructed on the proper application of the treatments. The application frequency and dosage will be as follows:

- Hydrophilic Methacrylate Gel (HM Gel): Participants in the experimental group will be instructed to apply HM Gel to the surgical site two times a day, in the morning and evening, for the duration of the two-week treatment period.
- Beta Sitosterol Ointment (BSO): Participants in the control group will be instructed to apply BSO to the surgical site two times a day, in the morning and evening, also for the duration of the two-week treatment period.
- The application process will be explained to each participant, emphasizing the importance of consistent and thorough application. Adherence to the treatment regimen will be monitored through regular follow-up visits. These follow-up visits will coincide with the baseline assessment, occurring at recruitment, and subsequent visits at Day 5 and Day 12 postpartum. The administration of the assigned treatments will commence immediately following the surgical procedure, either episiotomy or cesarean section, and continue for a period of two weeks. During this period, the participants will be instructed on the proper application of the treatments. The application frequency and dosage will be as follows:
  - Hydrophilic Methacrylate Gel (HM Gel): Participants in the experimental group will be instructed to apply HM Gel to the surgical site two times a day, in the morning and evening, for the duration of the two-week treatment period.

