## HMC RESEARCH PROTOCOL

- Beta Sitosterol Ointment (BSO): Participants in the control group will be instructed to apply BSO to the surgical site two times a day, in the morning and evening, also for the duration of the two-week treatment period.
- The application process will be explained to each participant, emphasizing the importance of consistent and thorough application. Adherence to the treatment regimen will be monitored through regular follow-up visits. These follow-up visits will coincide with the baseline assessment, occurring at recruitment, and subsequent visits at Day 5 and Day 12 postpartum.
- Phone Call Reminders by a trained staff to assess adherence of application. (Script is added in documentation in ABHATH)

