#### **Blinding:**

We will be blinding the tube ointments to ensure impartiality in the assessment of efficacy between the two treatments. This adjustment will enable us to minimize potential biases and ensure the integrity of our results.

The ointment tubes will be packaged in identical outer packaging, such as opaque boxes, to conceal any distinguishing features.

This approach will ensure that the participants nor the assessors of wound know which

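### Blinding of participants and wound assessors is promised outright, but identical outer packaging is the only measure described, and it cannot secure that blinding once the product is in use

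*Combined protocol and SAP*

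**What the plan says.** The blinding text appears twice in almost the same words: in Section 7 under Blinding, and in Section 10 under Randomization and Allocation Concealment. It has three parts.

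- A general intention: "We will be blinding the tube ointments to ensure impartiality in the assessment of efficacy between the two treatments".
- One concrete measure: "The ointment tubes will be packaged in identical outer packaging, such as opaque boxes, to conceal any distinguishing features".
- The property claimed to follow: "This approach will ensure that the participants nor the assessors of wound know which ointment is being used".

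Both sections also say that the data analysts will be blinded.

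Section 6, under the details of the interventions, has each woman apply her own product for two weeks. For the experimental arm: "Participants in the experimental group will be instructed to apply HM Gel to the surgical site two times a day". For the control arm: "Participants in the control group will be instructed to apply BSO to the surgical site two times a day". The same section monitors adherence at the follow-up visits, on Days 5 and 12, and adds phone calls on Days 3 and 7. Section 3 says of the hospital's usual practice that "emollient, moisturizer such as betasitosterol is commonly used for scar management".

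Under Outcomes, the primary outcome is wound healing. The secondary outcomes include pain ("We will assess pain levels using standardized pain scales") and satisfaction ("Patient satisfaction will be assessed through questionnaires to gauge the subjective experience and level of satisfaction with the treatment"). Scar appearance is also secondary, and Section 4 specifies POSAS for it, which has a patient part and an observer part.

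**The concern.** The protocol promises a result, that neither participants nor assessors will know the product, and gives as its basis a measure that stops working when the box is opened. Nothing further is described: no relabelling or sleeving of the tube, no matching of the products in look, smell or consistency, no separation of the assessor from the product, and no check on whether blinding held.

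Two things are at stake. First, pain, satisfaction and the patient part of POSAS are reported by the woman who handles the product, so a belief about which product she has can move those scores without any treatment effect. Blinding the analysts does not undo bias that is already in the data. Second, if a wound assessor learns the arm, the primary rating is exposed too, because a healed or not healed call involves judgement. A report that repeated the blinding claim as written would tell readers more than the described method supports.

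**Working it through.** **Step 1. Set the claim against the method.** The documents contain no figure to reproduce here, so the main check is a reading.

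| Question | What the documents give |
|---|---|
| Who is said to be blinded? | Participants, wound assessors and analysts (Sections 7 and 10) |
| Is the tube said to be blinded? | Yes, as an intention; no method at tube level |
| What concrete measure is described? | Identical outer packaging, with opaque boxes as the example |
| Who handles the product? | The participant, twice daily for two weeks (Section 6) |
| Are the two products said to look or feel alike? | Not addressed; they are named as a gel and an ointment |
| What protects the assessor? | Only the packaging; no rule on tubes or conversation at visits |

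**Step 2. Exposure of the participant.** 2 applications a day × 14 days = 28 applications, all with the box open and the tube in hand.

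**Step 3. Exposure of the assessor.** Days 5 and 12 are the only post-baseline visits described. Adherence is monitored at those visits. The note under the exclusion criteria also has healthcare providers ask then about other medications and supplements. The plan therefore prompts conversation about what the woman is applying, and does not say that someone other than the wound assessor holds it.

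**Step 4. Illustration of what expectation bias could do.** The documents give no size for such a bias, so the shift b, in SD units of a patient-reported score, is an assumption with range 0.1 to 0.3. Other inputs:

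- No true treatment effect.
- Significance level 0.05 (Statistical Analysis Plan). The plan does not state sidedness; two-sided is assumed.
- 53 per group within each surgery type (sample size text, Section 6).
- Pooled case: about 60 per group (Sample Size Adjustment) × 2 surgery types × (1 − 0.10 dropout) = 108 evaluable per arm.

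Both sizes are shown because the sample size text treats the surgery types separately, while the analysis text compares two treatment groups and can be read as pooled.

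With n per group, the test statistic is approximately normal with mean m = b × √(n/2) and SD 1, so

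P(significant) = P(Z > 1.96 − m) + P(Z < −1.96 − m).

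| n per group | b | m | P(significant), normal | P(significant), t-test |
|---|---|---|---|---|
| 53 | 0.1 | 0.1 × √26.5 = 0.515 | 0.0742 + 0.0067 = 0.081 | 0.080 |
| 53 | 0.2 | 1.030 | 0.1761 + 0.0014 = 0.178 | 0.175 |
| 53 | 0.3 | 1.544 | 0.3388 + 0.0002 = 0.339 | 0.334 |
| 108 | 0.1 | 0.1 × √54 = 0.735 | 0.1103 + 0.0035 = 0.114 | 0.113 |
| 108 | 0.2 | 1.470 | 0.3120 + 0.0003 = 0.312 | 0.310 |
| 108 | 0.3 | 2.205 | 0.597 + 0.000 = 0.597 | 0.593 |

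Against a nominal 5%, the rates are about 8%, 17.5% and 33% at 53 per group, and about 11%, 31% and 60% at 108 per arm. The calculation is symmetric: a shift favouring the control product gives the same rates in the other direction.

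**The case against.** The strongest reply is that the protocol does more than box the product. Both sections open by saying that the tubes will be blinded, so a masked tube may well be intended and only its description is missing. A reader might infer that only the box is masked and that the trial is in effect open-label for participants. The documents do not support that, for these reasons:

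- Tube blinding is declared. What is missing is how it will be done.
- The tubes' labels and the products' colour, smell and consistency are not described. The experimental product is called both a gel and Hemagel Ointment, so the name alone does not prove a tell-tale texture.
- The design is parallel-group. Each woman uses one product and has nothing to compare it with, and noticing a texture is not the same as knowing the allocation.
- Local use of beta-sitosterol describes hospital practice. It does not show that participants would recognise the product.

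A reader might also infer that any bias must favour the newer product. That depends on how the two products are presented to women. The consent form is not among the pages available, and nothing can be concluded from its absence.

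It is also fair to say that the patient-reported outcomes are secondary, that POSAS has an observer part, that analysts are blinded separately, and that the protocol never calls itself double-blind.

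All of this limits how far the criticism goes, but it does not remove it. The protocol does not merely leave a detail open. It asserts that the approach will secure blinding of two parties, and the one measure it describes cannot do so during two weeks of self-application.

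**Conclusion.** The claim is wrong as written and should be corrected. Participant blinding is not assured by the method described. Assessor unblinding is a risk that the plan leaves unguarded; the documents do not show that it happens. The exposed outcomes are pain, satisfaction and the patient part of POSAS. The primary wound rating is affected only if assessors learn the arm.

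The size and direction of any bias are unknown. The false-positive rates above show only that a modest shift could produce a significant patient-reported difference at either sample size. They rest on the assumed 0.1 to 0.3 SD, no true effect, a two-sided test, and, for 108 per arm, pooling of the surgery types with 10% dropout.

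**What to change.** 1. **Mask the tube.** Replace reliance on the outer box with an identical opaque over-label or sleeve on every tube, carrying only the study code, and describe it in Sections 7 and 10.
2. **Protect the wound assessor.** Keep tubes, and any discussion of the product or of adherence, away from the person rating the wound. The existing Day 3 and Day 7 calls can carry adherence questions. Anything that must be done at a visit, including handling tubes, should fall to someone other than the assessor.
3. **Restate the claim.** In place of the guarantee, say that wound assessors and analysts are blinded, and that tubes are masked but participants may recognise the formulation.
4. **Label the results to match.** Unless the two formulations are shown to be indistinguishable, report pain, satisfaction and patient POSAS with the statement that participant blinding was not assured.
5. **Optional.** Record the participant's and the assessor's guess of the allocation once, at the last visit.

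The cost is labels or sleeves, a few sentences of protocol text, some reallocation of tasks at visits and, if item 5 is adopted, one guess question each for participant and assessor. The downside is a weaker blinding claim, but an accurate one. Masking needs to be in place before enrolment, since it cannot be added afterwards for women already treated.
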